- A targeted physical examination, including an assessment for signs suggestive of PIMMCs, may be performed, if indicated based on review of interim medical history, by a study clinician licensed to make medical diagnoses and listed on the Form FDA 1572 as the site PI or sub-investigator.
- Approximately 8 mL of venous blood will be collected for cellular immunology assays.
- Approximately 16 mL of venous blood will be collected for future research.

8.2.5 Clinic Visit, Treatment Arms 2, 3, 5, and 6

Visit 06, Day 22 (Window: Day 22+7 days post first study vaccination), Treatment Arms 2, 3, 5, and 6

- Interim medical history, including an assessment for new medical conditions, stability of chronic diseases and symptoms suggestive of PIMMCs, will be obtained by interview of subjects and any changes since the previous clinic visit or phone call will be noted.
- All concomitant medications (including solicitation for receipt of any non-study influenza vaccines) will be recorded on the appropriate DCF.
- All AE/SAEs will be recorded on the appropriate DCF.
- A targeted physical examination, including an assessment for signs suggestive of PIMMCs, may be performed, if indicated based on review of interim medical history, by a study clinician licensed to make medical diagnoses and listed on the Form FDA 1572 as the site PI or sub-investigator.
- Approximately 15 mL of venous blood will be collected for serological assays.

- Approximately 16 mL of venous blood will be collected for future research.

8.2.6 Safety Follow-up, Phone Call, Treatment Arms 2, 3, 5, and 6

Visit 07, Day 61 (Window: Day 61±7 days post first study vaccination), Treatment Arms 2, 3, 5, and 6

Subjects will be contacted by phone to query for safety events and concomitant medications (including solicitation for receipt of any non-study influenza vaccines). AEs limited to SAEs and MAAEs, including NOCMCs and PIMMCs, that have occurred since the previous clinic visit or phone call will be solicited. Based on the information collected, subjects may be asked to return to the clinic for evaluation.

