- A urine or serum pregnancy test will be performed locally by the site within 24 hours prior to the second study vaccination for all women of childbearing potential. Results must be negative and known prior to the second study vaccination.
- Approximately 10 mL of venous blood will be collected immediately prior to the second study vaccination for clinical safety labs (WBC, Hgb, PLT, ALT, T. Bili, Cr) to be performed by the central (clinical) laboratory. The results from these evaluations will not be available or reviewed prior to the second study vaccination.
- Approximately 15 mL of venous blood will be collected immediately prior to the second study vaccination for serological assays.
- Approximately 32 mL of venous blood will be collected immediately prior to the second study vaccination for cellular immunology assays.
- Approximately 16 mL of venous blood will be collected immediately prior to the second study vaccination for future research.
- Pre-administration reactogenicity assessments will be performed immediately prior to the second study vaccination to establish baseline.
- Subjects will then receive one- 0.5 mL dose of study vaccine via a single IM injection into the deltoid muscle of the subjects' preferred arm. The second study vaccination may be given in the same preferred arm as long as there is no interference with the reactogenicity assessment. The site of injection (right or left arm) and time of study vaccine administration to the subject will be recorded on the appropriate DCF. Subjects will be observed in the clinic for at least 20 minutes after the second study vaccination.

The second study vaccination site will be examined, post-administration reactogenicity assessments will be performed, and any AE/SAEs will be recorded on the appropriate DCF prior to discharge from the clinic.

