4. INVESTIGATIONAL PLAN

4.1. Overall Study Design and Plan

DMID Protocol 17-0078 follows a Phase II randomized, partially-blinded study design enrolling males and non-pregnant females aged 19 to 50 years of age, inclusive, who are in good health as determined by medical history and physical examination, and meet all eligibility criteria, including erythrocyte sedimentation rate (ESR), hematology, and biochemistry parameter within acceptable range, and negative urine or serum pregnancy test (for females). This clinical trial is designed to assess the safety, reactogenicity and immunogenicity of one or two vaccinations of monovalent inactivated split influenza 2013 and 2017 A/H7N9 virus vaccines (2013 and 2017 A/H7N9 IIVs) manufactured by Sanofi Pasteur (SP), administered intramuscularly at different dosages (3.75 or 15 mcg of HA per dose), given with or without AS03 adjuvant manufactured by GlaxoSmithKline Biologicals (GSK), using different heterologous and homologous prime-boost vaccination schedules.

Subjects will be randomly assigned to 1 of 6 study groups with equal allocation 1:1:1:1:1:1 (see [Table 1](#)). Subjects assigned to Groups 1, 2, and 3 will receive an adjuvanted 2013 A/H7N9 IIV on Day 1 while those in Groups 4, 5, and 6 receive an adjuvanted 2017 A/H7N9 IIV on Day 1. Subjects assigned to Groups 1 and 4 will return approximately 21 days after their first vaccination to receive an adjuvanted 2017 A/H7N9 IIV. Subjects assigned to Groups 2,3,5, and 6 will return approximately after 120 days to receive their second vaccination of 2017 A/H7N9 IIV with or without AS03.

Reactogenicity will be measured by the occurrence of solicited injection site and systemic reactions from the time of each study vaccination through 7 days after each study vaccination. Unsolicited non-serious AEs will be collected from the time of each study vaccination through approximately 21 days after each study vaccination. SAEs and MAAEs, including NOCMCs and PIMMCs, will be collected from the time of the first study vaccination through approximately 12 months after the last study vaccination. Clinical laboratory evaluations for safety will be performed on venous blood collected prior to each study vaccination and approximately 7 days after each study vaccination.

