4.4.5. Selection and Timing of Dose for Each Subject

Each subject is to be randomly assigned to a study group which will define the number and timing of 2013 and/or 2017 A/H7N9 vaccinations. The first vaccination for all subjects takes place on the day of randomization and will include vaccination with AS03 adjuvanted 2013 A/H7N9 IIV (Groups 1,2,3) or AS03 adjuvanted 2017 A/H7N9 IIV (Groups 4,5,6). The second vaccination of 2017 A/H7N9 IIV takes place approximately 21 days after the first vaccination for Groups 1 and 4 (protocol defined window of 21-28 days post first vaccination), and approximately 120 days after the first vaccination for Groups 2, 3, 5, and 6 (protocol defined window of 113-134 days post first vaccination).

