8.2. Secondary Immunogenicity Analyses

The secondary immunogenicity endpoints HAI and Neut seroconversion, percentage of subjects with titer ≥ 40 , and GMTs against the 2013 and 2017 A/H7N9 vaccine viruses prior to each study vaccination, 21 days after the first vaccination and 180 days after the second vaccination will be summarized as described above. No formal hypothesis testing is planned.

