8.3.2. HAI and Neut Regression Modeling

Regression modeling will be utilized to test for the effect of treatment variables i.e. prime boost combination (*PrimeBoost*), Boost dose (*BoostDose*), and interval between vaccinations (*Interval*), on immune response. Logistic regression will be fit for the seroconversion outcome. If the available titer data meet the required assumptions of normality after log transformation, multiple linear regression will be fit to log-transformed titers. Separate models will be fit for each assay (HAI, Neut), each strain (2013 A/H7N9, 2017 A/H7N9) and each time point (Day 22 post vaccination 1, Day 22 post vaccination 2, Day 181 post vaccination 2). All models will be fit with a similar structure for *PrimeBoost*, *BoostDose*, *Interval*, and covariates, for the PP population. The treatment variables will be defined as *PrimeBoost* (homologous, heterologous), *BoostDose* (3.75 mcg+AS03, 15 mcg), and *Interval* (21 days, 120 days). All models will be fit with and without adjustment for the following covariates (*Z*): age in years, sex (female, male), BMI (<30, ≥ 30), and prior receipt of seasonal influenza vaccine in the current season (did not receive 2018-2019 seasonal influenza vaccine, received 2018-2019 seasonal influenza vaccine) (did not receive 2016-2017 or 2017-2018 seasonal influenza vaccines, received 2016-2017 and/or 2017-2018 seasonal influenza vaccine). The models as shown below assume a linear relationship between age in years and both probability of seroconversion and GMT. The validity of this assumption will be assessed prior to analysis and, if the relationship between age and response is found to be non-linear, adjustments will be made to model parameters to satisfy regression assumptions. Modeling assumptions will be checked using standard diagnostic methods (e.g., using the INFLUENCE option in PROC LOGISTIC or PROC GLM). Parameter estimates and odds ratio estimates for the logistic models will be presented for the 2013 and 2017 A/H7N9 strains without covariate adjustment in Table 64, Table 65, Table 66, Table 67, and with covariate adjustment in Table 68, Table 69, Table 70, Table 71. Parameter estimates for the multiple linear regression models will be presented for the 2013 and 2017 A/H7N9s strain without covariate adjustment in Table 72, Table 73, Table 74, Table 75, and with covariate adjustment in Table 76, Table 77, Table 78, Table 79.

Model 1A: Logistic Regression (without covariate adjustment):

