$$\begin{aligned} \text{logit}[P(\text{seroconversion})] \\ = \beta_0 + \beta_1 \times \text{PrimeBoost} + \beta_2 \times \text{BoostDose} + \beta_3 \times \text{Interval} \\ + \beta_4 \times (\text{PrimeBoost} * \text{BoostDose}) + \beta_5 \times (\text{PrimeBoost} * \text{Interval}) + \varepsilon \end{aligned}$$

Model 1B: Logistic Regression (with covariate adjustment):

$$\begin{aligned} \text{logit}[P(\text{seroconversion})] &= \beta_0 + \beta_1 \times \text{PrimeBoost} + \beta_2 \times \text{BoostDose} + \beta_3 \times \text{Interval} \\ &+ \beta_4 \times (\text{PrimeBoost} * \text{BoostDose}) + \beta_5 \times (\text{PrimeBoost} * \text{Interval}) + \beta_6 \times Z + \varepsilon \end{aligned}$$

Model 2A: Multiple Linear Regression (without covariate adjustment):

$$\begin{aligned} \log(\text{titer}) &= \beta_0 + \beta_1 \times \text{PrimeBoost} + \beta_2 \times \text{BoostDose} + \beta_3 \times \text{Interval} \\ &+ \beta_4 \times (\text{PrimeBoost} * \text{BoostDose}) + \beta_5 \times (\text{PrimeBoost} * \text{Interval}) + \varepsilon \end{aligned}$$

Model 2B: Multiple Linear Regression (with covariate adjustment):

$$\begin{aligned} \log(\text{titer}) &= \beta_0 + \beta_1 \times \text{PrimeBoost} + \beta_2 \times \text{BoostDose} + \beta_3 \times \text{Interval} + \beta_4 \times (\text{PrimeBoost} * \text{BoostDose}) \\ &+ \beta_5 \times (\text{PrimeBoost} * \text{Interval}) + \beta_6 \times Z + \varepsilon \end{aligned}$$

Where Z is the matrix of covariates age, sex, BMI, and prior receipt of seasonal influenza vaccine as defined in Section 6.4. Subjects missing data for one or more covariates will be excluded from Models 1B and 2B.

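### SAP 8.3.2 models boost dose and interval on the Day 22 post vaccination 1 serum, which is drawn before the boost in every arm, so four of its five treatment terms cannot have an effect at that visit

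*SAP*

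**What the plan says.** SAP 8.3.2 sets out to test three treatment variables: PrimeBoost (homologous or heterologous), BoostDose (3.75 mcg with AS03, or 15 mcg) and Interval (21 or 120 days). Models 1A and 1B are logistic for seroconversion. Models 2A and 2B are linear for log titer, to be fitted if the normality assumption is met. The B versions add covariates. Each model has five treatment terms: the three main effects, PrimeBoost by BoostDose, and PrimeBoost by Interval. Separate models are planned for each assay, each strain and "each time point (Day 22 post vaccination 1, Day 22 post vaccination 2, Day 181 post vaccination 2". On their form the section says "All models will be fit with a similar structure for" these variables and the covariates, in the per protocol (PP) population.

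On timing:

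- Groups 1 and 4 receive dose 2 at Visit 06. Protocol 8.2.7 states: "Approximately 15 mL of venous blood will be collected immediately prior to the second study vaccination for serological assays".
- For the other arms, Protocol 8.2.5 schedules "Visit 06, Day 22 (Window: Day 22+7 days post first study vaccination), Treatment Arms 2, 3, 5, and 6", with serology and no vaccination. SAP 4.1 says "Groups 2,3,5, and 6 will return approximately after 120 days to receive their second vaccination".
- The first vaccination, per SAP 4.4.5, "will include vaccination with AS03 adjuvanted 2013 A/H7N9 IIV (Groups 1,2,3) or AS03 adjuvanted 2017 A/H7N9 IIV (Groups 4,5,6". SAP Table 1 gives 3.75 mcg with AS03 for all six first doses.

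SAP 8.2 covers the secondary endpoints, which in SAP 3.2.2 include the titers about 21 days after the first vaccination. It states: "No formal hypothesis testing is planned".

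The regression shells (SAP Tables 64-79) are all titled for 21 or 180 days after the second vaccination. The Table 64 shell takes 15 mcg and 21 days as reference levels. Its implementation note fits interactions first and drops them if they are not significant.

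**The concern.** A model term for a treatment that nobody has yet received has a true value of zero in a randomized trial. A p-value for it can only be a correct null or a false positive, and a false positive at this visit would carry the label of boost dose or schedule. The same visit offers a clean randomized comparison of 2013 and 2017 priming, and the priming effect of the different vaccines is a stated goal in SAP section 2. The written model is a poor vehicle for that comparison, because its PrimeBoost coefficient changes meaning and precision with the reference coding and with whether interactions stay in.

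**Working it through.** 1. **The plan's own figure.** Protocol Table 14 (SAP Table 8) gives detectable differences for 27 v 27, two-sided likelihood ratio test, alpha 0.05, 80% power. Enumerating all pairs of outcomes and rejecting when G > 3.841 gives power of 0.816 (0.10 v 0.42), 0.794 (0.20 v 0.55), 0.805 (0.30 v 0.68), 0.813 (0.40 v 0.77) and 0.801 (0.50 v 0.84). The table reproduces. It describes one arm against one arm.

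2. **Treatment received by the Day 22 draw.**

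| Groups | Given so far | Dose 2 |
|---|---|---|
| 1 | 2013, 3.75 mcg + AS03 | after this draw, same visit |
| 2, 3 | 2013, 3.75 mcg + AS03 | about Day 121, 121 − 22 = 99 days later |
| 4 | 2017, 3.75 mcg + AS03 | after this draw, same visit |
| 5, 6 | 2017, 3.75 mcg + AS03 | about Day 121, 99 days later |

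In SAP Table 1 every boost is the 2017 vaccine, so PrimeBoost is in effect a label for priming antigen: 3 × 30 = 90 v 90. The other four terms correspond to nothing that has happened.

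3. **Null tests.** Models at this visit: 2 assays × 2 strains × 2 outcomes × 2 (with and without covariates) = 16.
   - Interactions kept: 16 × 4 = 64 null tests; 64 × 0.05 = 3.2 expected false positives.
   - Interactions dropped throughout: 16 × 2 = 32; 32 × 0.05 = 1.6.
   - If titers fail the normality check and only logistic models are fitted, these halve to 32 (1.6) and 16 (0.8).
   - The tests are correlated, but that does not change the expected count. In 20,000 simulated null trials of the linear model (30 per arm), at least one of the four null terms was significant in 14.5%, and at least one interaction in 8.9%.

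4. **Precision of the PrimeBoost coefficient.** Let s be the SD of log titer, n = 30 per arm, and let m solve Var = 2s²/m, so that m v m is the equivalent two-group comparison. The full model has six coefficients for six arms.
   - Shells' reference levels (15 mcg, 21 days; no arm received this): b₁ = (G1 − G2 + G3) − (G4 − G5 + G6). Var = 6s²/30, SE = 0.447s, m = 10.
   - Any occupied arm pair as reference, for example b₁ = G1 − G4: Var = 2s²/30, SE = 0.258s, m = 30.
   - Interactions dropped: b₁ = mean(G1, G2, G3) − mean(G4, G5, G6). Var = 2s²/90, SE = 0.149s, m = 90.
   - With 10% excluded from PP (27 per arm), m becomes 9, 27 and 81.

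5. **What that means for detection.** On log titer at 80% power, (1.960 + 0.842) × SE gives 1.25s (m = 10), 0.72s (m = 30) and 0.42s (m = 90). For proportions, the asymptotic likelihood ratio formula at comparator rates of 10% to 50% gives about 0.33 to 0.38 for 27 v 27 and 0.17 to 0.22 for 81 v 81.

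**The case against.** The strongest reply is that no table is planned for this model. SAP 8.3.2 sends its results to Tables 64-79, and all sixteen concern the period after the second vaccination. The extra time point may be a slip in the text, with no display in which a spurious term would appear. This stands as a limit on the harm. It does not make the text correct: the SAP then contradicts itself on whether the models are run, and the written instruction is to run them.

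The second reply concerns precision. A reader might infer that the priming comparison is simply cut to 30 v 30 and loses two thirds of its data. The documents do not support that as a flat statement. Under the Table 64 note, non-significant interactions are removed and PrimeBoost then uses all 90 v 90. In the null simulation that would happen about 91% of the time. The 30 v 30 figure needs retained interactions and an occupied reference arm; the shells' own coding with retained interactions gives the 10 v 10 equivalent. The note does not cure the main defect, because BoostDose and Interval remain after the interactions go.

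Third, the regression sits under exploratory analyses, SAP 6.8 disclaims any designed null hypothesis, and the SAP 8.2 sentence can be read as governing the secondary summaries only. A reader might see a flat contradiction between 8.2 and 8.3.2. It is better described as an ambiguity about the same serum that one sentence would remove.

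Finally, SAP Tables 24-31 already give GMT, fold rise, titer ≥1:40 and seroconversion at this visit by arm with confidence intervals, so the priming data are reported, though not pooled.

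**Conclusion.** The point holds for the model as written. At Day 22 post vaccination 1, four of the five treatment terms have no possible effect. The cost is up to 64 null tests with about 3.2 expected false positives, or 32 and about 1.6 with interactions dropped. The loss of precision for priming antigen is conditional: none if interactions are dropped, a 30 v 30 or 10 v 10 equivalent if they are kept. Text and shells also disagree on whether this visit is modelled.

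A reader might infer that this threatens the trial's main conclusions. It does not. The primary endpoints are 21 days after the second vaccination, when the boost has been given, and nothing in the documents makes a primary estimate or a decision on trial conduct depend on the Day 22 post vaccination 1 models. Severity is minor to moderate.

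Assumptions: equal arm sizes, common variance, reference-cell coding as in the shells, tests at their nominal 5% level, and the plan's 10% PP exclusion. The two-group equivalents are exact for the linear model and indicative for the logistic one.

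**What to change.** In SAP 8.3.2, remove Day 22 post vaccination 1 from the time points of Models 1A-2B. At that visit fit instead a model with one treatment term, priming antigen (Groups 1-3 v Groups 4-6, about 90 v 90), and add a matching shell.

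Define its covariates by status before the Day 22 sample. The planned 2018-2019 seasonal vaccine covariate cannot be carried over unchanged: the notes to the Table 56, 68 and 76 shells count receipt at any time before the second study vaccination, which in Groups 2, 3, 5 and 6 runs to about Day 121. For this model, count receipt only up to the Day 22 draw.

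Amend SAP 8.2 so that it agrees with whatever testing is kept on this serum. Pooled columns for 2013 and 2017 priming in the Day 22 post vaccination 1 rows of Tables 24-31 would be useful but are optional.

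The cost is SAP wording and one new shell format. No new data are needed and conduct does not change. Protocol 11.6 requires the SAP to be final before unblinding for any analysis, so the change belongs before that point.

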Height and weight will be collected at the screening visit (optional) or on Day 1 prior to the first study vaccination for the calculation of BMI.

Reactogenicity assessments will include an assessment of solicited AEs occurring from the time of each study vaccination through 7 days after each study vaccination, which includes an

assessment of injection site reactions including pruritus (itching), ecchymosis (bruising), erythema (redness), induration (hardness), edema (swelling), pain, and tenderness as well as systemic reactions including fever, feverishness (chills/shivering/sweating), fatigue (tiredness), malaise (general unwell feeling), myalgia (body aches/muscular pain exclusive of the injection site), arthralgia (joint pain exclusive of the injection site), headache, and nausea. Pre-administration reactogenicity assessments will be performed immediately prior to each study vaccination to establish baseline, then the study vaccination will be given.

Subjects will be observed in the clinic for at least 20 minutes after each study vaccination. The study vaccination site will be examined, post-administration reactogenicity assessments will be performed, and any AE/SAEs will be recorded on the appropriate DCF prior to discharge from the clinic. The study vaccination site will also be examined approximately 1, 3 and 7 days after each study vaccination.

All subjects will complete a Memory Aid from the time of each study vaccination through 7 days after each study vaccination. Memory Aids will be reviewed with the subjects for any AEs (solicited injection site and systemic reactions as well as unsolicited AEs), SAEs and concomitant medications (including solicitation for receipt of any non-study influenza vaccines) approximately 1, 3 and 7 days after each study vaccination via phone call or clinic visit.

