3.1.3. Exploratory

Immunogenicity:

- To assess the effects of age, sex, body mass index (BMI), and prior receipt of seasonal or non-study pandemic influenza vaccine(s) on serum HAI and Neut antibody responses following receipt of the second study vaccine.
- To assess the neuraminidase (NA) content of the 2013 and 2017 A/H7N9 IIVs and determine, in at least a subset of samples, the serum antibody responses to N9 NA.
- To assess, in at least a subset of samples, HA stem-specific antibody responses.
- To assess, in at least a subset of samples, the cross-reactivity of serum HAI and Neut antibody responses to antigenically drifted variants of influenza A/H7 viruses.
- To assess, in at least a subset of samples, the frequency of influenza-specific (A/H7N9 antigens) IgA, IgG and IgM memory B cells (MBCs).
- To assess, in at least a subset of samples, the frequency of influenza-specific (A/H7N9 antigens) IgA, IgG and IgM plasmablasts (antibody-secreting cells [ASCs]).
- To assess, in at least a subset of samples, the multifunctional cytokine/chemokine profile of influenza A/H7N9-specific CD4 and CD8 T cells.

- To assess, in at least a subset of samples, the characterization of circulating T follicular helper (cT_{FH}) cells.
- To assess, in at least a subset of samples, the study vaccine-induced changes in populations and/or activation status of innate immune cells (monocytes, dendritic cells [DCs] and natural killer [NK] cells).
- To assess, in at least a subset of samples, the study vaccine-induced activation status of B cells.
- To assess, in at least a subset of samples, the B cell receptor repertoire and degree of somatic hypermutation generated in response to study vaccination.

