6.4. Covariates and Subgroups

As a protocol defined exploratory analysis, HAI antibody response following the second vaccination will be summarized stratified by the following covariates: age (categorical: 19-34, 35-50), sex (male, female), body mass index (<30, ≥30), and prior receipt of seasonal influenza vaccine(s). Prior receipt of influenza vaccines, including any reported prior receipt of A/H5 vaccinations, or reported seasonal vaccination receipt will also be included as covariates. Summaries of prior seasonal vaccination will include breakdowns of receipt of the two seasonal vaccinations prior to study initiation (did not receive 2016-2017 or 2018-2019; received 2016-2017 and/or 2018-2019) as well as independently assessing subject receipt of 2018-2019 seasonal vaccine (did not receive/received) prior to the second dose of study vaccine. These covariates will be considered in statistical modeling as described in Section 8.3. As these analyses are exploratory, the study was not powered for any subgroup analyses.

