9.1. Demographic and Other Baseline Characteristics

Summaries of age, sex, ethnicity, race, BMI, and prior receipt of seasonal influenza vaccine will be presented by site ([Table 19](#), [Table 20](#)) and by study group ([Table 21](#), [Table 22](#)). Age will be summarized as a continuous variable. Ethnicity is categorized as Hispanic or Latino, or not Hispanic and not Latino. In accordance with NIH reporting policy, subjects may self-designate as belonging to more than one race or may refuse to identify a race, the latter reflected in the electronic case report form (eCRF) as “No” to each racial option. BMI will be summarized as a continuous as well as categorical variable, categorized as (<30, ≥30). Self-reported history of prior receipt of influenza vaccines will be broken down by the following categories: receipt of seasonal vaccines for prior seasons (2016-2017, 2017-2018), receipt of seasonal vaccine for the current season (2018-2019; considered up to receipt of study dose 2), and receipt of any A/H5 vaccines prior to enrollment. Demographic information for individual subjects will be provided in [Listing 6](#). Subjects’ prior influenza vaccination history (seasonal and non-seasonal) will be provided in [Listing 8](#).

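### The adjusted regression models cut BMI at 30 while age stays continuous, which under stated assumptions loses about 36–51% of the information on the exploratory BMI coefficient

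*SAP*

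**What the plan says.** SAP 8.3.2 fits logistic models for seroconversion (1A, 1B) and linear models for log titer (2A, 2B). The B versions add covariates: age in years, then "sex (female, male), BMI (<30, ≥ 30), and prior receipt of seasonal influenza vaccine in the current season", followed by vaccination in the two preceding seasons. The shells for Tables 68 and 76 show the same two BMI rows.

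Age is handled differently. The section states that "The models as shown below assume a linear relationship between age in years and both probability of seroconversion and GMT", that this will be checked, and that the model will be adjusted if the check fails. In the stratified summaries age is itself cut, at 19–34 and 35–50 (SAP 6.4 and 8.3.1), so the SAP uses classes for tables and years for models.

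The continuous BMI value is on hand. Protocol 7.1 collects height and weight at screening or "prior to the first study vaccination for the calculation of BMI", and SAP 9.1 says "BMI will be summarized as a continuous as well as categorical variable" (continuous in Tables 20 and 22). Protocol 5.1 sets no BMI limit for entry.

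The exploratory objective in SAP 3.1.3 begins "To assess the effects of age, sex, body mass index (BMI), and prior receipt of seasonal or non-study pandemic influenza vaccine(s" and concerns HAI and Neut responses after the second vaccination. SAP 6.4 adds: "As these analyses are exploratory, the study was not powered for any subgroup analyses".

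**The concern.** A two-class covariate treats BMI 29.9 and 30.1 as different and BMI 30 and 45 as the same. If response changes gradually with BMI, the test of the BMI effect is weaker and its interval wider, in relative terms, than the collected data allow. Tables 68–71 and 76–79 are where the BMI effect receives an estimate, a standard error, an interval and a p-value, so a null result there could be read as evidence that BMI does not matter.

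The SAP's own treatment of age shows that the alternative is already accepted practice in this plan.

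**Working it through.** **The plan's own figures.** The documents state no precision or power for the BMI effect. The nearest figure is the minimum detectable difference between two arms (SAP Table 8, protocol Table 14: 27 per arm, two-sided likelihood ratio test, alpha 0.05, 80% power). Exact enumeration of that test at the five listed pairs gives 81.6%, 79.4%, 80.5%, 81.3% and 80.1%, so the table reproduces. It concerns arms, not BMI.

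**Inputs.** Enrolment is up to 180, with up to 10% excluded from the per-protocol analysis (SAP 5), giving 6 × 27 = 162. SAP 8.3.2 names the per-protocol population. SAP 8.3 would use mITT if exclusions do not exceed 10%, in which case the base could be as large as 180. The share q with BMI ≥30 is not given; the assumed range is 20–50%.

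**Formula.** For a linear effect of a normal covariate cut so that a share q lies above the cut, the information kept relative to the continuous covariate is

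R(q) = φ(z)² / [q(1 − q)], where z is the standard normal point with upper tail q and φ is the normal density.

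Example, q = 0.30: z = 0.524, φ(z) = 0.348, so R = 0.1209 / 0.21 = 0.576, a loss of 42%.

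| Share ≥30 | Kept, R | Lost | 162 × R |
|---|---|---|---|
| 20% | 0.490 | 51% | 79 |
| 25% | 0.539 | 46% | 87 |
| 30% | 0.576 | 42% | 93 |
| 35% | 0.603 | 40% | 98 |
| 40% | 0.622 | 38% | 101 |
| 50% | 0.637 | 36% | 103 |

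The loss at 50% is the minimum under normality. A share of 15% would lose 57%. With all 180 analysed, shares of 25–40% would be equivalent to 97–112 subjects.

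**Skewed BMI.** Lognormal BMI with means of 26–30 and SDs of 5–7 gives losses of 37–44%.

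**In terms of power.** Assume a BMI–log titer correlation of 0.22 (not a document figure) and N = 162. With the Fisher transformation, power with continuous BMI is Φ(atanh(0.22) × √159 − 1.96) = 0.805. With the cut, 0.22 is multiplied by √R, and power falls to 0.50, 0.57 and 0.60 at shares of 20%, 30% and 40%. Simulating a regression built like Model 2B (six arms, the three treatment variables, both interactions and two further covariates) gave 79–80% with continuous BMI against 49%, 55% and 58%, with information ratios of 0.48, 0.57 and 0.61.

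**Treatment terms.** At the same correlation, residual variance is 1 − 0.22² = 0.952 with continuous BMI and 1 − 0.60 × 0.22² = 0.971 with a cut keeping 60%. The ratio of standard errors is √(0.971 / 0.952) = 1.01, about 1%.

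**The case against.** The strongest reply is that little rests on this coefficient. The endpoint attached to the objective (SAP 3.2.3) is GMT and seroconversion broken down by BMI, which needs classes, and Tables 48–55 deliver it. The regression is there to test the treatment variables, with BMI as one adjuster; the protocol says only that covariates may be considered in modelling. One prespecified cut, used throughout, keeps tables and models describing the same groups, and the SAP claims no power for subgroups. A linear term carries an assumption of its own.

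Much of this stands and limits the weight of the point. It does not remove it: SAP 6.4 carries these covariates into the models, and the shells report the BMI estimate with a p-value. A two-class term also imposes a form, a step at exactly 30, and the SAP plans no check of it. Low power is no reason to discard information already collected.

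Two stronger readings are tempting and should be resisted. A reader might infer a fixed loss of about 40%. The documents give no BMI distribution and no shape of effect; 40% is reached only at a share of about 34% under linearity and normality. A reader might also infer that the cut harms the treatment comparison. Arms are randomised, so unmodelled BMI variation does not confound in expectation, the precision cost is about 1% at the assumed correlation, and Models 1A and 2A omit BMI altogether.

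**Conclusion.** The point holds as a minor improvement. Entering BMI only as <30 or ≥30 loses about 36–51% of the information on its coefficient. This rests on a roughly linear effect, roughly normal BMI and 20–50% of subjects at or above 30. The formula belongs to the linear models (2B) and is an approximation for the logistic ones (1B). If the true effect is a step at 30, the loss is zero. What can be gained is a more informative estimate for one exploratory objective; the primary and secondary immunogenicity results do not depend on this coding.

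**What to change.** In SAP 8.3.2 (Models 1B and 2B) and the shells for Tables 68–71 and 76–79, replace the two BMI rows with one continuous term, for example per 5 kg/m². Extend the linearity check and remedy written for age to BMI. Keep <30 and ≥30 for the stratified summaries in Tables 48–55, as the SAP does with age classes, and restrict the covariate definition in SAP 6.4 accordingly.

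The cost is SAP and shell wording only. Nothing new is collected, and the protocol names BMI as a covariate without a cut-point, so it needs no amendment. The downside is an assumed linear form, subject to the check.
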